HAQ-DI	
A questionnaire validated for RA self-assessment by subjects that contains 20 questions in the following 8 functional areas:
 
 • Dressing and grooming • Arising

Term	Definition
	
 • Eating • Walking • Hygiene • Reach • Grip • Common daily activities 
Scoring within each functional area is from 0 (without any difficulty) to 3 (unable to do). The total score is obtained by summing 8 area scores and dividing by 8. The total HAQ-DI score ranges from 0 to 3 and corresponds to the current degree of disability:
 
 • 0 to < 1 Mild difficulties to moderate disability • 1 to < 2 Moderate disability • 2 to 3 Severe to very severe disability 
A HAQ-DI score reduction by 0.22 represents the MCID.

hsCRP	Marker of systemic inflammation associated with disease activity in RA that is generally not detectable with routine CRP assays.
ITT population	Primary analysis population comprising all enrolled and randomized subjects.
PTE population	Subjects from ITT population who received the assigned treatment through Week 12, have no major procedural protocol deviations, and for whom follow-up data are available.
RA disease activity assessments	
A standardized set of RA assessments that should be performed in the following order:
 
 • HAQ-DI • SGA • Subject's pain • TJC28 • SJC28 • EGA • hsCRP (mg/L)
RAMRIS	
A standardized method for MRI acquisition of the hand and wrist, joint pathology definitions and a scoring system for semiquantitative evaluation of:
 
 • Synovitis. 8 joints each scored on a scale from 0 (normal) to 3 (severe), resulting in a total score from 0 to 24 • Bone erosion. 25 bones each scored on a scale from 0 to 10, resulting in a total score from 0 to 250. Change by > 0.5 represents disease progression. • Osteitis. 25 bones each scored on a scale from 0 to 3, resulting in a total score from 0 to 75 • CARLOS (cartilage loss). 25 joints each scored on a scale from 0 to 4, resulting in a total score from 0 to 100
Randomization	Process of randomly assigning subjects to a treatment or control group which occurs after completion of Day 0 assessments.

Term	Definition

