17.8 Analysis Populations

The interim and primary efficacy analyses at Week 12 will be conducted on the intent-to-treat (ITT) population. Exploratory analyses will be performed on the ITT and per-treatment-evaluable (PTE) populations through Week 12 and on the open-label and cross-over PTE populations during the open-label, long-term follow-up. The safety will be evaluated on the safety population. All analysis populations are defined below:

- *ITT population.* All enrolled and randomized subjects in Stage 1 and 2.
- *PTE population.* Subjects from ITT population who received the assigned treatment through Week 12, have no major procedural protocol deviations (see Section 18.2.2), and for whom follow-up data through Week 12 are available.
- *Treatment to Open Label (TOL) population.* Treatment subjects from ITT population who received active stimulation through Week 12, completed Week 12 assessments, continued to receive active stimulation during open-label follow-up, and for whom follow-up data are available.
- *Control to Open Label (COL) population.* Control subjects from ITT population who received non-active (sham) stimulation through Week 12, switched to active stimulation after completing Week 12 assessments, continued to receive active stimulation during open-label follow-up, and for whom follow-up data are available.
- *Safety population.* All enrolled subjects.

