5.2 Analysis Populations

Analysis population defines the subjects to be included in an analysis. The primary efficacy analyses for the primary and key secondary endpoints will be conducted on the intent-to-treat (ITT) and per-treatment-evaluable (PTE) populations. The exploratory analyses will be conducted on the ITT population as detailed in **Table 4**. All analysis populations are defined below:

- *ITT population.* All enrolled and randomized subjects in Stage 1 and 2.
- *PTE population.* Subjects from ITT population who have received the assigned treatment, who have no major procedural protocol deviations (see Section 9.2) and for whom follow-up data are available.
- *Safety population.* All enrolled subjects in Stage 1 and 2.

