Variable	Treatment (N=xxx)	Control (N=xxx)
ACR20 Response from baseline on the day of informed consent		
Week 12		
N [1]	xx	xx
Yes	xx (xx.x%)	xx (xx.x%)
Difference [2]	xx.x%	
95% CI for difference [2]	(xx.x, xx.x)	
p-value for difference [2]	0.xxx	
ACR20 Response from Day 0*		
Week 12		
N [1]	xx	xx
Yes	xx (xx.x%)	xx (xx.x%)
Difference [2]	xx.x%	
95% CI for difference [2]	(xx.x, xx.x)	
p-value for difference [2]	0.xxx	

Abbreviations: ACR, American College of Rheumatology; CI, confidence interval; ITT, intent to treat.

[1] Percentage calculated based on ITT population.

[2] Difference in proportions and one-sided p-value based on the Cochran-Mantel-Haenszel test stratified by inadequate response or loss of response to JAKi and RA disease severity at Day 0 for Stage 1 subjects and RA disease severity at Day 0 and inadequate response or loss of response to ≥ 4 biological DMARDs with ≥ 2 mechanisms of action for Stage 2 subjects.

*Day 0 post-Implant Procedure and before randomization and initiation of assigned treatment

Reference: Listing 16.x.x.x

SOURCE: xxxxx SAS 9.4 {program location} {run date/time}

CONFIDENTIAL

48 of 158

May not be reproduced outside of SetPoint Medical without written permission from Document Control.

Table 14.1.2.1.1
 Sensitivity Analysis of ACR20 Response: Rescue Treatment
 (ITT Population)

Variable	Treatment (N=xxx)	Control (N=xxx)
ACR20 Response from baseline on the day of informed consent		
Week 12		
N [1]	xx	xx
Yes	xx (xx.x%)	xx (xx.x%)
Difference [2]	xx.x%	
95% CI for difference [2]	(xx.x, xx.x)	
p-value for difference [2]	0.xxx	
ACR20 Response from Day 0		
Week 12		
N [1]	xx	xx
Yes	xx (xx.x%)	xx (xx.x%)
Difference [2]	xx.x%	
95% CI for difference [2]	(xx.x, xx.x)	
p-value for difference [2]	0.xxx	

Abbreviations: ACR, American College of Rheumatology; ITT, intent to treat.

[1] Percentage calculated based on ITT Population.

[2] Difference in proportions and one-sided p-value based on the Cochran-Mantel-Haenszel test stratified by inadequate response or loss of response to JAKi and RA disease severity at Day 0 for Stage 1 subjects and RA disease severity at Day 0 and inadequate response or loss of response to ≥ 4 biological DMARDs with ≥ 2 mechanisms of action for Stage 2 subjects.

*Day 0 post-Implant Procedure and before randomization and initiation of assigned treatment

Reference: Listing 16.x.x.x

SOURCE: xxxxx SAS 9.4 {program location} {run date/time}}

Table 14.1.2.1.2

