DAS28-CRP moderate/good EULAR response at Week 12 from Day 0		
Week 12		
N [1]	xx	xx
Yes	xx (xx.x%)	xx (xx.x%)
Difference [2]	xx.x%	
95% CI for difference [2]	(xx.x%, xx.x%)	
p-value for difference [2]	0.xxx	
DAS28-CRP response (MCID \geq -1.2) at Week 12		
Week 12		
N [1]	xx	xx
Yes	xx (xx.x%)	xx (xx.x%)
Difference [2]	xx.x%	
95% CI for difference [2]	(xx.x%, xx.x%)	
p-value for difference [2]	0.xxx	
HAQ-DI response (MCID \geq -0.22) at Week 12		
Week 12		
N [1]	xx	xx
Yes	xx (xx.x%)	xx (xx.x%)
Difference [2]	xx.x%	
95% CI for difference [2]	(xx.x%, xx.x%)	
p-value for difference [2]	0.xxx	
Mean HAQ-DI score change at Week 12		
Week 12		
N [1]	xx	xx
Yes	xx (xx.x%)	xx (xx.x%)
Difference [2]	xx.x	
95% CI for difference [2]	(xx.x, xx.x)	
p-value for difference [2]	0.xxx	

Abbreviations: ACR, American College of Rheumatology; CRP, C-reactive protein; DAS, Disease Activity Score; EULAR, European League Against Rheumatism; HAQ-DI, Health Assessment Questionnaire Disability Index; ITT, intent to treat; MCID, minimal clinically important difference.

Variable	Treatment (N=xxx)	Control (N=xxx)
[1] Percentage calculated based on ITT Population.		
[2] Difference in proportions and one-sided p-value based on the Cochran-Mantel-Haenszel test stratified by inadequate response or loss of response to JAKi and RA disease severity at Day 0 for Stage 1 subjects and RA disease severity at Day 0 and inadequate response or loss of response to ≥ 4 biological DMARDs with ≥ 2 mechanisms of action for Stage 2 subjects.		

Reference: Listing 16.x.x.x

SOURCE: xxxx SAS 9.4 {program location} {run date/time} }

Table 14.1.2.2.2
 Sensitivity Analysis of Key Secondary Endpoints: Timing of Baseline
 (ITT Population)

Variable	Treatment (N=xxx)	Control (N=xxx)
DAS28-CRP moderate/good EULAR response at Week 12 from Day 0		
Week 12		
N [1]	xx	xx
Yes	xx (xx.x%)	xx (xx.x%)
Difference [2]	xx.x%	
95% CI for difference [2]	(xx.x%, xx.x%)	
p-value for difference [2]	0.xxx	
DAS28-CRP response (MCID \geq -1.2) at Week 12 from Day 0		
Week 12		
N [1]	xx	xx
Yes	xx (xx.x%)	xx (xx.x%)
Difference [2]	xx.x%	
95% CI for difference [2]	(xx.x%, xx.x%)	
p-value for difference [2]	0.xxx	
HAQ-DI response (MCID \geq -0.22) at Week 12 from Day 0		
Week 12		
N [1]	xx	xx
Yes	xx (xx.x%)	xx (xx.x%)
Difference [2]	xx.x%	
95% CI for difference [2]	(xx.x%, xx.x%)	
p-value for difference [2]	0.xxx	
Mean HAQ-DI score change at Week 12 from Day 0		
Week 12		
N [1]	xx	xx
Yes	xx (xx.x%)	xx (xx.x%)
Difference [2]	xx.x	

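### The SAP's supportive PTE analysis does not match the SAP's own endpoint definitions or protocol 17.8

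*SAP*

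**What the plan says.** **Definition.** Protocol 17.8 admits to PTE "Subjects from ITT population who received the assigned treatment through Week 12, have no major procedural protocol deviations" and requires subjects "for whom follow-up data through Week 12 are available". Protocol section 3 keeps the Week 12 limit for treatment but sets none for the data: "Subjects from ITT population who received the assigned treatment through Week 12, have no major procedural protocol deviations, and for whom follow-up data are available". SAP 5.2 has neither limit: "Subjects from ITT population who have received the assigned treatment, who have no major procedural protocol deviations", with follow-up data available at no stated time. The footnotes to SAP Table 14.1.1.1 and Listing 16.1.2.3 repeat the SAP form.

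**Role.** Protocol 17.8 puts the interim and primary efficacy analyses on ITT and adds: "Exploratory analyses will be performed on the ITT and per-treatment-evaluable (PTE) populations through Week 12". SAP 5.2 says that the primary efficacy analyses of the primary and key secondary endpoints "will be conducted on the intent-to-treat (ITT) and per-treatment-evaluable (PTE) populations". SAP 8.3.3 places the primary analysis on ITT.

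**Tables.** SAP Table 4 marks the primary endpoint and all four key secondary endpoints for PTE. Two PTE efficacy shells serve this: Table 14.1.2.1.0 (ACR20) and Table 14.1.2.2.1 (key secondary endpoints). The first footnote of each reads "1] Percentage calculated based on ITT population", apart from a capital letter. SAP 5.1 sets n, the subjects providing data, as the general denominator. The first row of Table 14.1.2.2.1 is "DAS28-CRP moderate/good EULAR response at Week 12 from Day 0".

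**The concern.** A per-treatment analysis shows whether the ITT result holds among subjects who were treated and followed as planned. For that, it must use the same endpoints as the ITT analysis, a denominator from its own population, and a definition that removes those who stopped early. The SAP departs from each of these in one place.

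If the shells are programmed literally, one of the four key secondary endpoints, EULAR response from informed consent, has no PTE analysis at all. The PTE percentages are too low by the share of subjects excluded. Subjects who stopped before Week 12 may be counted as per-treatment. The wording in SAP 5.2 also leaves unclear what a PTE result is for if it differs from ITT.

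**Working it through.** **1. Endpoints: what is marked for PTE against what the shells carry.**

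| Endpoint | Marked for PTE (SAP Table 4) | Defined baseline (SAP 8.3.1, 8.4.1, 8.5) | PTE shell | Baseline in shell |
|---|---|---|---|---|
| ACR20 | yes | consent | 14.1.2.1.0 | consent |
| ACR20 from Day 0 | yes | Day 0 | 14.1.2.1.0 | Day 0 |
| EULAR good/moderate | yes | consent | 14.1.2.2.1 | **Day 0** |
| DAS28-CRP MCID | yes | consent | 14.1.2.2.1 | none named; consent by the note to SAP Table 5 |
| HAQ-DI MCID | yes | consent | 14.1.2.2.1 | none named; consent by the same note |
| Mean HAQ-DI change | **no** | consent (exploratory, SAP 8.6) | 14.1.2.2.1 | none named |

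The other PTE shells (14.1.2.16.1, 14.1.2.17.1, 14.1.2.18.1) concern blinding, so EULAR response from consent appears in no PTE shell. EULAR response from Day 0 is the timing-of-baseline sensitivity analysis (SAP 8.5.1, Table 14.1.2.2.2). Table 14.1.2.2.1 names the same four endpoints in the same order as that sensitivity shell, including mean HAQ-DI change with a yes/no percentage row. This suggests copying, but that is an inference.

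**2. Denominator.** The plan gives no PTE figure to reproduce. The inputs are the SAP 3.4 design values: 60% and 30% response, 125 per arm. As a check on reading them, a simulation of 1,000,000 trials with the Stage 1 futility rule gave power 0.958 (stated 0.959) and stopping probability 0.040 (stated 0.040). Those figures are not in dispute.

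Let p be the response rate in PTE and e the share of an arm excluded from PTE. The displayed rate with the ITT denominator is p × (1 − e). The documents do not give e, so 0% to 20% is assumed, with PTE rates of 60% and 30%.

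| Excluded, treatment / control | Displayed rates | Gap between displayed rates |
|---|---|---|
| 0% / 0% | 60.0% / 30.0% | 30.0 |
| 5% / 5% | 57.0% / 28.5% | 28.5 |
| 10% / 10% | 54.0% / 27.0% | 27.0 |
| 20% / 20% | 48.0% / 24.0% | 24.0 |
| 10% / 5% | 54.0% / 28.5% | 25.5 |
| 5% / 10% | 57.0% / 27.0% | 30.0 |

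In counts, at 20%: 125 × 0.8 = 100 PTE subjects with 60 responders. This is 60/100 = 60% on PTE but 60/125 = 48% on ITT. With the PTE denominator every line reads 60% and 30%.

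**3. Definition.** Take a subject who withdraws after a Week 4 assessment. Under protocol 17.8 the subject is out on both limits. Under SAP 5.2 the subject has received assigned treatment and has some follow-up data. The three major procedural deviations in SAP 9.2 (procedure before consent, treatment inconsistent with assignment, treated while no longer eligible) do not plainly cover early stopping. The subject can therefore stay in. Missing Week 12 data then count as non-response (SAP 5.8.1; NRI in Table 4), which pulls PTE back towards ITT. Steps 2 and 3 do not add up: the more early stoppers PTE keeps, the smaller e becomes.

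**4. Role.** SAP 8.3.3 puts the primary test on ITT. Table 14.1.2.2, which holds the Hochberg-adjusted p-values, is headed ITT. No SAP text makes PTE a condition for success or for a claim.

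**The case against.** The strongest reply is that these are editorial slips in a supportive analysis. Much of that stands.

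- A reader might infer that the PTE tables are not per-treatment at all. The documents do not support this. Both shells are headed PTE, and the difference and p-value fall under the second footnote (the CMH test), which does not send them to ITT. The first footnote governs displayed percentages. Whether the displayed difference would follow those percentages is not stated.
- A reader might infer that ACR20 from Day 0 is left out of PTE because Table 14.1.2.2.1 omits it. It is analysed in Table 14.1.2.1.0.
- The ITT footnote also sits under adverse event tables headed Safety Population and conflicts with SAP 5.1, so it is probably carried-over text.
- This SAP covers data through Week 12, so receipt of assigned treatment can be read as meaning that whole period. That is fair, but the protocol states the limit and the SAP does not. The protocol itself is not uniform: section 3 lacks the data limit found in 17.8.
- SAP 8.4, 8.4.1 and 8.5 fix the EULAR baseline clearly enough for a careful programmer to notice the row. That lowers the risk but leaves the shell wrong.

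**Conclusion.** The point holds as a consistency fault in supportive analyses. Followed literally, the shells leave EULAR response from informed consent without a PTE analysis and lower each displayed PTE percentage by the factor (1 − e): 60% becomes 57% to 48% at an assumed 5% to 20% exclusion. The SAP 5.2 definition may keep early stoppers in PTE. The percentages rest on the assumed exclusion rates and on PTE rates equal to the design rates; with no exclusions there is no understatement.

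A reader might take the SAP 5.2 wording to make PTE a second primary analysis, or to put the trial's conclusion at risk. The documents do not support that: the success decision and the Hochberg procedure stay on ITT, and the confirmatory results are unaffected. The fault is minor, but worth correcting because the repair is small.

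**What to change.** 1. In Table 14.1.2.2.1, set the EULAR row to the informed-consent baseline. Remove mean HAQ-DI change or label it exploratory. Cross-refer to Table 14.1.2.1.0 for ACR20 from Day 0.
2. In Tables 14.1.2.1.0 and 14.1.2.2.1, state that percentages use the PTE population.
3. In SAP 5.2, and in the footnotes to Table 14.1.1.1 and Listing 16.1.2.3, restore the protocol 17.8 definition with both Week 12 limits.
4. In SAP 5.2, name ITT as the set for the primary and key secondary analyses and PTE as supportive.

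The cost is a few lines of SAP text, two shells and two footnotes, with no new data and no change to sample size or to the confirmatory tests. It belongs before lock of the primary dataset, because SAP 5.1 classes analyses designed after lock as post hoc.

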8.6.1 Definitions of Exploratory Secondary Endpoints

ACR50/70 response at Week 12

ACR50/70 response corresponds to 50% and 70% improvement at Week 12 from baseline on the day of informed consent, respectively, in TJC28 and SJC28 and 3 out of 5 ACR core measures and follows the same general and statistical analyses as for ACR20 (see Section 8.3.1).

Component 20/50/70 response

20/50/70 response for each component (TJC28, SJC28, Subject Pain, SGA, HAQ-DI, EGA, hsCRP) corresponds to 20, 50 and 70% improvement from baseline to Week 12, respectively (see Section 8.2), and follows the same general and statistical analyses as for ACR20 (see Section 8.3.1).

DAS28-CRP score change and LDA/remission

The Disease Activity Score (DAS) is a derived measurement of 4 components with differential weighting:

- TJC28
- SJC28
- hsCRP (mg/L)
- SGA

A total score ranges from 0 to 10 and is computed as follows:

$$\text{DAS28-CRP} = 0.56 * \text{sqrt}(\text{TJC28}) + 0.28 * \text{sqrt}(\text{SJC28}) + 0.36 * \text{ln}(\text{CRP}+1) + 0.014 * \text{SGA} + 0.96$$

If one of the components is missing at an individual assessment point, the DAS28-CRP value for that assessment will be set to missing. An alternative imputation method for missing components may be applied as described in Section 8.1.

The DAS28-CRP score corresponds to the current RA activity:

- 0 to < 2.6 Remission
- 2.6 to < 3.2 Low disease activity (LDA)
- 3.2 to \leq 5.1 Moderate activity
- > 5.1 High activity

If one of the components is missing at a given assessment point, no imputations will be done, and the DAS28-CRP value for that assessment will be set to missing.

CDAI LDA/remission and MCID response at Week 12

The Clinical Disease Activity Index (CDAI) is a composite score consisting of the sum of:

- SJC28
- TJC28
- SGA/10
- EGA/10

The CDAI score is calculated as follows and ranges from 0 to 76 with higher values representing higher disease activity:

- CDAI = TJC28 + SJC28 + SGA + EGA

The CDAI score corresponds to the current RA activity:

- 0 to \leq 2.8 Remission
- >2.8 to \leq 10 Low disease activity (LDA)
- >10 to \leq 22 Moderate activity
- >22 High activity

The MCID varies depending on RA activity at baseline:

- -12 for high activity
- -6 for moderate activity
- 1 for low activity

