8.6.2 Analysis of Exploratory Secondary Endpoints

The following endpoints will be analyzed with the CMH test, as described in Section **5.1**:

- ACR50/70 response at Week 12
- DAS28-CRP LDA/remission at Week 12
- CDAI response at Week 12
- HAQ-DI response at Week 12
- EQ-5D-5L response at Week 12
- RAMRIS bone erosion progression (> 0.5) at Week 12

The MMRM will be used to analyze the following endpoints, as described in Section **5.1**:

- Mean CDAI score change from baseline to Week 12
- Mean HAQ-DI score change from baseline to Week 12
- Mean EQ-5D-5L score change from baseline to Week 12
- Mean SF-36/PCS/MCS score change from baseline to Week 12
- Mean RAMRIS bone erosion, osteitis, synovitis, and CARLOS score change from baseline to Week 12
- Percent change in plasma biomarkers (e.g., IL-6, SAA, MMP3)

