Min-Max	xxx.x – xxx.x	xxx.x – xxx.x
Day 0		
N [1]	xx (xx.x%)	xx (xx.x%)
Mean (SD)	xxx.x (xxx.xx)	xxx.x (xxx.xx)
Median	xxx.xx	xxx.xx
Min-Max	xxx.x – xxx.x	xxx.x – xxx.x
Change from baseline		
N [1]	xx (xx.x%)	xx (xx.x%)
Mean (SD)	xxx.x (xxx.xx)	xxx.x (xxx.xx)
Median	xxx.xx	xxx.xx
Min-Max	xxx.x – xxx.x	xxx.x – xxx.x
95% CI for difference [2]	(xx.x, xx.x)	
p-value for difference [2]	0.xxx	
Week 4		
N [1]	xx (xx.x%)	xx (xx.x%)
Mean (SD)	xxx.x (xxx.xx)	xxx.x (xxx.xx)
Median	xxx.xx	xxx.xx
Min-Max	xxx.x – xxx.x	xxx.x – xxx.x
Change from baseline		
N [1]	xx (xx.x%)	xx (xx.x%)
Mean (SD)	xxx.x (xxx.xx)	xxx.x (xxx.xx)
Median	xxx.xx	xxx.xx
Min-Max	xxx.x – xxx.x	xxx.x – xxx.x

CONFIDENTIAL

May not be reproduced outside of SetPoint Medical without written permission from Document Control.

91 of 158

Variable	Treatment (N=xxx)	Control (N=xxx)
95% CI for difference [2]	(xx.x, xx.x)	
p-value for difference [2]	0.xxx	
Week 8		
N [1]	xx (xx.x%)	xx (xx.x%)
Mean (SD)	xxx.x (xxx.xx)	xxx.x (xxx.xx)
Median	xxx.xx	xxx.xx
Min-Max	xxx.x – xxx.x	xxx.x – xxx.x
Change from baseline		
N [1]	xx (xx.x%)	xx (xx.x%)
Mean (SD)	xxx.x (xxx.xx)	xxx.x (xxx.xx)
Median	xxx.xx	xxx.xx
Min-Max	xxx.x – xxx.x	xxx.x – xxx.x
95% CI for difference [2]	(xx.x, xx.x)	
p-value for difference [2]	0.xxx	
Week 12		
N [1]	xx (xx.x%)	xx (xx.x%)
Mean (SD)	xxx.x (xxx.xx)	xxx.x (xxx.xx)
Median	xxx.xx	xxx.xx
Min-Max	xxx.x – xxx.x	xxx.x – xxx.x
Change from baseline		
N [1]	xx (xx.x%)	xx (xx.x%)
Mean (SD)	xxx.x (xxx.xx)	xxx.x (xxx.xx)
Median	xxx.xx	xxx.xx
Min-Max	xxx.x – xxx.x	xxx.x – xxx.x
95% CI for difference [2]	(xx.x, xx.x)	
p-value for difference [2]	0.xxx	
DAS28-CRP MCID Response (score reduction from Baseline by 1.2) [1]		
Week 12		
N [1]	xx	xx
Yes	xx (xx.x%)	xx (xx.x%)
Difference [2]	xx.x%	

CONFIDENTIAL

May not be reproduced outside of SetPoint Medical without written permission from Document Control.

92 of 158

Variable	Treatment (N=xxx)	Control (N=xxx)
95% CI for difference [2]	(xx.x, xx.x)	
p-value for difference [2]	0.xxx	
 DAS28-CRP Low Disease Activity (score 2.6 to < 3.2) [1]		
Week 12		
N [1]		
Yes	xx (xx.x%)	xx (xx.x%)
Difference [2]	xx.x%	
95% CI for difference [2]	(xx.x, xx.x)	
p-value for difference [2]	0.xxx	
 DAS28-CRP Remission (score 0 to < 2.6) [1]		
Week 12		
N [1]	xx	xx
Yes	xx (xx.x%)	xx (xx.x%)
Difference [2]	xx.x%	
95% CI for difference [2]	(xx.x, xx.x)	
p-value for difference [2]	0.xxx	
 DAS28-CRP EULAR Good Response [1][3]		
Week 12		
N [1]	xx	xx
Yes	xx (xx.x%)	xx (xx.x%)

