Difference [2]	xx.x%	
95% CI for difference [2]	(xx.x, xx.x)	
p-value for difference [2]	0.xxx	
 DAS28-CRP EULAR Moderate Response [1][4]		
Week 12		
N [1]	xx	xx
Yes	xx (xx.x%)	xx (xx.x%)
Difference [2]	xx.x%	
95% CI for difference [2]	(xx.x, xx.x)	
p-value for difference [2]	0.xxx	

Abbreviations: CRP, C-reactive protein; DAS, Disease Activity Score; EULAR, European League Against Rheumatism; ITT, intent to treat.

[1] Percentage calculated based on ITT Population

CONFIDENTIAL

May not be reproduced outside of SetPoint Medical without written permission from Document Control.

93 of 158

Variable	Treatment (N=xxx)	Control (N=xxx)
[2] Difference in mean score change from baseline and one-sided p-value based on the Mixed-effect Model Repeated Measure model with PROC MIXED. Difference in proportions and one-sided p-value based on the Cochran-Mantel-Haenszel test. Stratification factors are inadequate response or loss of response to JAKi and RA disease severity at Day 0 for Stage 1 subjects and RA disease severity at Day 0 and inadequate response or loss of response to ≥ 4 biological DMARDs with ≥ 2 mechanisms of action for Stage 2 subjects.		
[3] EULAR good treatment response if DAS28-CRP score reduced from baseline to a given timepoint by > 1.2 and is ≤ 3.2 at a given timepoint		
[4] EULAR moderate treatment response if DAS28-CRP score reduced from baseline to a given timepoint by > 0.6 to ≤ 1.2 , and is ≤ 5.1 at a given timepoint; or DAS28-CRP score reduced from baseline to a given timepoint by > 1.2 , and is > 3.2 at a given timepoint		

Reference: Listing 16.x.x.x

SOURCE: xxxxx SAS 9.4 {program location} {run date/time}}

Table 14.1.2.12
 CDAI
 (ITT Population)

	Treatment (N=xxx)	Control (N=xxx)
CDAI Score		
Screening (baseline)		
N [1]	xx (xx.x%)	xx (xx.x%)
Mean (SD)	xxx.x (xxx.xx)	xxx.x (xxx.xx)
Median	xxx.xx	xxx.xx
Min-Max	xxx.x – xxx.x	xxx.x – xxx.x
Day 0		
N [1]	xx (xx.x%)	xx (xx.x%)
Mean (SD)	xxx.x (xxx.xx)	xxx.x (xxx.xx)
Median	xxx.xx	xxx.xx
Min-Max	xxx.x – xxx.x	xxx.x – xxx.x
Change from baseline		
N [1]	xx (xx.x%)	xx (xx.x%)
Mean (SD)	xxx.x (xxx.xx)	xxx.x (xxx.xx)
Median	xxx.xx	xxx.xx
Min-Max	xxx.x – xxx.x	xxx.x – xxx.x
95% CI for difference [2]	(xx.x, xx.x)	
p-value for difference [2]	0.xxx	
Week 4		
N [1]	xx (xx.x%)	xx (xx.x%)
Mean (SD)	xxx.x (xxx.xx)	xxx.x (xxx.xx)
Median	xxx.xx	xxx.xx
Min-Max	xxx.x – xxx.x	xxx.x – xxx.x
Change from baseline		
N [1]	xx (xx.x%)	xx (xx.x%)
Mean (SD)	xxx.x (xxx.xx)	xxx.x (xxx.xx)
Median	xxx.xx	xxx.xx

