Min-Max	xxx.x – xxx.x	xxx.x – xxx.x

CONFIDENTIAL

May not be reproduced outside of SetPoint Medical without written permission from Document Control.

95 of 158

	Treatment (N=xxx)	Control (N=xxx)
95% CI for difference [2]	(xx.x, xx.x)	
p-value for difference [2]	0.xxx	
Week 8		
N [1]	xx (xx.x%)	xx (xx.x%)
Mean (SD)	xxx.x (xxx.xx)	xxx.x (xxx.xx)
Median	xxx.xx	xxx.xx
Min-Max	xxx.x – xxx.x	xxx.x – xxx.x
Change from baseline		
N [1]	xx (xx.x%)	xx (xx.x%)
Mean (SD)	xxx.x (xxx.xx)	xxx.x (xxx.xx)
Median	xxx.xx	xxx.xx
Min-Max	xxx.x – xxx.x	xxx.x – xxx.x
95% CI for difference [2]	(xx.x, xx.x)	
p-value for difference [2]	0.xxx	
Week 12		
N [1]	xx (xx.x%)	xx (xx.x%)
Mean (SD)	xxx.x (xxx.xx)	xxx.x (xxx.xx)
Median	xxx.xx	xxx.xx
Min-Max	xxx.x – xxx.x	xxx.x – xxx.x
Change from baseline		
N [1]	xx (xx.x%)	xx (xx.x%)
Mean (SD)	xxx.x (xxx.xx)	xxx.x (xxx.xx)
Median	xxx.xx	xxx.xx
Min-Max	xxx.x – xxx.x	xxx.x – xxx.x
95% CI for difference [2]	(xx.x, xx.x)	
p-value for difference [2]	0.xxx	
CDAI Low Disease Activity (Score >2.8 to ≤ 10) [1]		
Screening (baseline)		
N [1]	xx	xx
Yes	xx (xx.x%)	xx (xx.x%)
Difference [2]	xx.x%	

CONFIDENTIAL

May not be reproduced outside of SetPoint Medical without written permission from Document Control.

96 of 158

	Treatment (N=xxx)	Control (N=xxx)
95% CI for difference	(xx.x, xx.x)	
p-value for difference [2]	0.xxx	
Week 12		
N [1]	xx	xx
Yes	xx (xx.x%)	xx (xx.x%)
Difference [2]	xx.x%	
95% CI for difference [2]	(xx.x, xx.x)	
p-value for difference [2]	0.xxx	
CDAI Remission (Score 0 to \leq 2.8) [1]		
Screening (baseline)		
N [1]	xx	xx
Yes	xx (xx.x%)	xx (xx.x%)
Difference [2]	xx.x%	
95% CI for difference [2]	(xx.x, xx.x)	
p-value for difference [2]	0.xxx	
Week 12		
N [1]	xx	xx
Yes	xx (xx.x%)	xx (xx.x%)
Difference [2]	xx.x%	
95% CI for difference [2]	(xx.x, xx.x)	
p-value for difference [2]	0.xxx	
CDAI Response (MCID) [1][3]		
Week 12		
N [1]	xx	xx
Yes	xx (xx.x%)	xx (xx.x%)
Difference [2]	xx.x%	
95% CI for difference [2]	(xx.x, xx.x)	
p-value for difference [2]	0.xxx	

Abbreviations: CDAI, Clinical Disease Activity Index; ITT, intent to treat; MCID, Minimal clinically important difference.

[1] Percentage calculated based on ITT Population.

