Min-Max	xxx.x – xxx.x	xxx.x – xxx.x
Week 24		
N [3]	xx (xx.x%)	xx (xx.x%)
Mean (SD)	xxx.x (xxx.xx)	xxx.x (xxx.xx)
Median	xxx.xx	xxx.xx
Min-Max	xxx.x – xxx.x	xxx.x – xxx.x
Change from baseline [4]		
N [3]	xx (xx.x%)	xx (xx.x%)
Mean (SD)	xxx.x (xxx.xx)	xxx.x (xxx.xx)
Median	xxx.xx	xxx.xx
Min-Max	xxx.x – xxx.x	xxx.x – xxx.x
95% CI	(xx.x, xx.x)	(xx.x, xx.x)
Repeat for:		
Week 36		
Week 48		
Week 60		
Week 72		
Week 84		
Week 96		
Week 108		
Week 120		
Week 132		
Week 144		
Week 156		
Week 168		

Variable	TOL [1] (N=xxx)	COL [2] (N=xxx)
Week 180		
Week 192		
DAS28-CRP low disease activity (score 2.6 to < 3.2)		
Week 24		
N	xx	xx
Yes [3]	xx (xx.x%)	xx (xx.x%)
95% CI	(xx.x, xx.x)	(xx.x, xx.x)
Repeat for:		
Week 36		
Week 48		
Week 60		
Week 72		
Week 84		
Week 96		
Week 108		
Week 120		
Week 132		
Week 144		
Week 156		
Week 168		
Week 180		
Week 192		
DAS28-CRP remission (score 0 to < 2.6)		
Week 24		
N	xx	xx
Yes [3]	xx (xx.x%)	xx (xx.x%)
95% CI	(xx.x, xx.x)	(xx.x, xx.x)
Repeat for:		
Week 36		
Week 48		
Week 60		
Week 72		
Week 84		

Variable	TOL [1] (N=xxx)	COL [2] (N=xxx)
Week 96		
Week 108		
Week 120		
Week 132		
Week 144		
Week 156		
Week 168		
Week 180		
Week 192		
 DAS28-CRP score change from initiation of stimulation [5]		
Day of initiation of stimulation [5]		
N [3]	xx (xx.x%)	xx (xx.x%)
Mean (SD)	xxx.x (xxx.xx)	xxx.x (xxx.xx)
Median	xxx.xx	xxx.xx
Min-Max	xxx.x – xxx.x	xxx.x – xxx.x
 Week 24		
Change from initiation of stimulation [5]		
N [3]	xx (xx.x%)	xx (xx.x%)
Mean (SD)	xxx.x (xxx.xx)	xxx.x (xxx.xx)
Median	xxx.xx	xxx.xx
Min-Max	xxx.x – xxx.x	xxx.x – xxx.x
95% CI	(xx.x, xx.x)	(xx.x, xx.x)
 Repeat for:		
Week 36		
Week 48		
Week 60		
Week 72		
Week 84		
Week 96		
Week 108		
Week 120		
Week 132		
Week 144		
Week 156		

Variable	TOL [1] (N=xxx)	COL [2] (N=xxx)
Week 168		
Week 180		
Week 192		

Abbreviations: CI, confidence interval; COL, Control to Open Label; CRP, C-reactive protein; DAS, Disease Activity Score; TOL, Treatment to Open Label;

- [1] Treatment to Open Label (TOL): The TOL population comprises treatment subjects from ITT population who received active stimulation through Week 12, completed Week 12 assessments, continued to receive active stimulation during open-label follow-up, and for whom follow-up data are available.

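### At Week 12 the SAP tests low disease activity as a band that excludes remission, so the LDA difference and its one-sided p-value do not measure benefit

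*SAP*

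**What the plan says.** SAP 8.6.1 divides DAS28-CRP into non-overlapping states. Remission is 0 to below 2.6, and the next state is given as "2.6 to < 3.2 Low disease activity (LDA" (closing bracket cut). Protocol Section 3 has the same categories. SAP 8.6.2 sends "DAS28-CRP LDA/remission at Week 12" to the CMH test in one bullet and does not say whether this is one combined endpoint or two. For CDAI, that list names only the response endpoint, not LDA.

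The Appendix B shells settle what would be printed. Table 14.1.2.11 has one row headed "DAS28-CRP Low Disease Activity (score 2.6 to < 3.2) [1" and another headed "DAS28-CRP Remission (score 0 to < 2.6) [1" (each ends in a cut-off footnote mark). Each has a difference, a 95% CI and a p-value, defined in the footnote as "Difference in proportions and one-sided p-value based on the Cochran-Mantel-Haenszel test". Table 14.1.2.12 has the parallel row "CDAI Low Disease Activity (Score >2.8 to ≤ 10) [1". No row in either table pools LDA with remission.

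The listing shells do not fit these bands. Listing 16.1.2.6.6, and its long-term counterpart 16.8.2.7.6 in CLP-008, label DAS28-CRP LDA with a lower bound of 0.6 instead of 2.6. Example records in the DAS28-CRP and CDAI listings of both SAPs (16.1.2.6.5, 16.1.2.6.6, 16.8.2.7.5, 16.8.2.7.6) mark the same visit Yes for LDA and Yes for remission. Exclusive bands make that impossible.

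**The concern.** A one-sided superiority test on a binary outcome assumes that Yes is better than No. In the LDA row, No combines moderate activity, high activity, subjects imputed as non-responders and subjects in remission. Moving a subject from moderate activity into the band helps the active arm. Moving a subject from the band into remission hurts it. The row's difference and p-value therefore cannot be read as evidence for or against benefit, although the label invites that reading.

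The conflicting listings add a programming risk. The DAS28-CRP formula in SAP 8.6.1 has a constant of 0.96 and no negative terms, so no score can fall below 0.96. A lower bound of 0.6 therefore amounts to any score below 3.2, which is LDA or better. A programmer who follows the listing label and one who follows the table label would produce different LDA flags from the same data.

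**Working it through.** **The plan's own figures.** Neither document states an LDA rate, power or sample size, so there is no LDA figure to reproduce. The sample size and sidedness come from SAP 3.4: 250 subjects, 125 per arm, one-sided 0.025. As a check on those inputs, take ACR20 rates of 50% versus 30% with the Stage 1 stop (30 per arm, stop if the difference is below 10 points) and 95 more per arm. Exact binomial enumeration with a pooled chi-square test gives power 0.774. The plan states 0.773.

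**Step 1: assumed counts, 125 per arm.** The documents give no Week 12 LDA or remission rates by arm, so these counts are illustrative. The test is the unstratified pooled z, with p taken from the upper tail:

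z = (pT − pC) / √[ p̄(1 − p̄) × 2/125 ]

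| Outcome | Active | Sham | Difference | z | One-sided p |
|---|---|---|---|---|---|
| Band only, as tabulated | 16 (12.8%) | 19 (15.2%) | −2.4 points | −0.55 | 0.71 |
| Remission | 34 (27.2%) | 15 (12.0%) | +15.2 points | 3.03 | 0.001 |
| LDA or better | 50 (40.0%) | 34 (27.2%) | +12.8 points | 2.14 | 0.016 |

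For the band, p̄ = 35/250 = 0.14, the standard error is √(0.14 × 0.86 × 0.016) = 0.0439, and z = −0.024/0.0439. The approximate 95% CI is −2.4 ± 1.96 × 4.39, or −11.0 to +6.2 points. That is an uninformative result with the wrong sign, not evidence for sham.

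**Step 2: counts set to the pilot's remission rate.** Protocol 16.7 reports two remissions in its account of the ten actively stimulated SPM-008 subjects. Assume 20% remission on active (25 of 125), 10 remissions on sham, and 10 versus 13 in the band.

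- Band: 8.0% versus 10.4%, p = 0.74.
- Remission: 20.0% versus 8.0%, p = 0.003.
- LDA or better: 28.0% versus 18.4%, p = 0.036.

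**Step 3: when reversal occurs.**

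*Mixture.* Treatment moves a fraction f of all subjects into remission, whatever their state would have been on sham. The active band rate is then (1 − f) × the sham band rate, always lower than sham. With sham band 8–15%, sham remission 5–10% and f 10–30%, the band difference runs from −0.8 to −4.5 points. Power of the band test is 0.1–1.4%; power of the LDA-or-better test is 26% to above 99%.

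*Uniform shift of a normal score.* The band is centred at (2.6 + 3.2)/2 = 2.9. With a sham mean above 2.9, reversal requires an active mean below 5.8 minus the sham mean. With SD 1.3:

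- Means 4.5 (sham) and 3.9 (active): the band rises from 8.7% to 13.6% (+4.9 points), while scores below 3.2 rise from 15.9% to 29.5% (+13.6 points). The effect is diluted, not reversed.
- Means 3.5 and 2.2: the band falls from 16.4% to 15.8%, while scores below 3.2 rise from 40.9% to 77.9%. The effect is reversed.

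**The case against.** Four points weigh against the concern.

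- **The benefit is still reported.** Remission has its own tested row, and in the first example its p-value is smaller than that for LDA or better. The bands are disjoint, so a reader can add the two percentages. This stands, but it supplies no CI or test for LDA or better and does not make the LDA p-value interpretable. The EULAR good-response row is no substitute, because it also requires a fall of more than 1.2.
- **Reversal is not the likely pattern at pilot-like means.** In SPM-005 the mean fell by 1.91 from 5.99, to about 4.08. Under a uniform shift, reversal at that active mean would need a sham mean below 5.8 − 4.08 = 1.72, which is not plausible. This stands: a modest uniform shift dilutes the effect, and reversal needs responders who move into remission or low means overall.
- **The SAP may intend the combined endpoint.** The single bullet in 8.6.2 and the listing examples can be read that way. This is fair on intent, but the table shells print the band alone. It supports reconciling the text rather than leaving it.
- **The bands are the protocol's own activity states.** They are sound as descriptive categories. The difficulty arises only when one of them is tested for superiority.

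**Conclusion.** The point holds for the Week 12 rows in Tables 14.1.2.11 and 14.1.2.12. LDA is tested there as a category not ordered with benefit, no row tests LDA or better, and text, tables and listings disagree on the definition. The size depends on rates the documents do not give. In the assumed examples the band p-value is 0.71 or 0.74, while LDA or better gives 0.016 or 0.036. The calculations are unstratified, so the planned CMH figures would differ somewhat.

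A reader might infer two stronger things that the documents do not support. The first is that the long-term tables carry the same inferential fault. CLP-008 Tables 14.8.2.11 and 14.8.2.12 use the same bands but report only counts, percentages and within-cohort CIs. They have no difference and no p-value, and both cohorts are on active stimulation, so there is no sham rate to fall below. The long-term issue is only consistent labelling.

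The second is that a trial claim is at risk. LDA is listed as an exploratory secondary endpoint (SAP 8.6) and lies outside the Hochberg family (SAP 8.5), so neither the primary result nor any key secondary claim depends on it. The correction is worth making because it is cheap, not because it changes the trial's conclusion.

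**What to change.** In SAP 8.6.1 and 8.6.2 and Tables 14.1.2.11 and 14.1.2.12:

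- Define the tested LDA response as DAS28-CRP below 3.2 and CDAI of 10 or less, so that it includes remission.
- Keep remission as a separate tested row.
- Show the exclusive bands only as descriptive activity states, without a p-value.
- State in 8.6.2 that LDA-or-better and remission are two endpoints, and add the CDAI versions to the CMH list.

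Correct the DAS28-CRP LDA label in Listings 16.1.2.6.6 and 16.8.2.7.6, and the CDAI LDA label in Listings 16.1.2.6.5 and 16.8.2.7.5. The example records marked Yes for both states are then consistent. Use the same definition for the descriptive rates in CLP-008 Tables 14.8.2.11 and 14.8.2.12.

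The cost is wording and a changed cut-point in the programs; no new data are needed. Under SAP 5.1, analyses designed after the dataset is locked are post hoc, so the change keeps its prespecified status only if made before lock.
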